#### **10.8.1.2 Exploratory biomarker**

For exploratory biomarkers [defined in Section 5.7.3.2], separate summaries of quantitative descriptive statistics for absolute values, absolute change and percent change from baseline are presented by analysis visit and treatment group (including geometric mean and associated 95% CI).

For exploratory biomarkers for which categories have been used, the number and percentage of subjects with a value in each category are summarized by analysis visit and treatment group.

### **10.9 Analysis of safety variables**

The SAF is used to perform all safety analyses.

For the tabulations by analysis visit and time points (e.g. values over time for blood pressure measurements, ECG), if multiple values are available (unscheduled visits/retests), the examination closest to the planned visit/ time point is chosen [see Section 11 for more details].

However, for the summaries of treatment-emergent abnormalities over the study period, all safety data collected up to EOS are considered.

All safety data are included in listings, with specific flags for the treatment-emergent or values taken into account in the analyses.

#### **10.9.1 Adverse events**

All AEs captured from signature of informed consent up to EOS are reported in the subject listings which include data collected in eCRF as well as the coded terms (SOC, PT) and a flag for treatment-emergent.

For displays of AEs summarizing counts on the event level (i.e. total number of events), the denominator for calculating percentage is the number AEs occurring in a given treatment group. For displays of events by period of onset, the denominator is the number of AEs occurring in a given treatment group during the relevant period of onset. For displays of AEs summarizing counts on the subject level (i.e. total number of subjects experiencing events), the denominator for percentages is the number of subjects in the SAF for a given treatment group.

For all tables, aggregate counts for total number of subjects, events and associated percentages, and total number of subjects, events and associated percentages per SOC and PT are also included (as applicable).

For tables presented by SOC and PT, SOCs/PTs are sorted by descending frequency of the number of subjects in the highest-dose group. If the frequencies of SOCs or PTs are the same, alphabetical order is used.

For tables presented by PT, PTs are sorted by descending frequency of the number of subjects in the highest-dose treatment group. If the frequencies of PTs are the same, alphabetical order is used.

The following displays of adverse events are provided:

- An overview of treatment-emergent adverse events (TEAEs) by treatment group with the following counts and percentages:
  - Subjects with at least one TEAE;
  - Subjects with at least one serious TEAE;
  - Subjects with fatal serious TEAE;
  - Subjects with at least one non-serious TEAE;
  - Subjects with at least one severe TEAE;
  - Subjects with at least one drug-related TEAE;
  - Subjects with at least one drug-related serious TEAE;
  - Subjects with at least one TEAE leading to study drug discontinuation.
- The number and percentage of TEAEs, and subjects experiencing TEAEs, by period of onset (on Day 1 post-dose, after Day 1, overall), treatment group, SOC and PT.
- The number and percentage of subjects with TEAEs by treatment group and PT.
- The number and percentage of subjects with related TEAEs, by treatment group and PT. If an adverse event (PT) occurs more than once for a subject during the treatment period, the strongest relationship to study treatment is taken into account.
- The number of subjects with TEAEs, by treatment group, severity/ intensity and PT. If an adverse event (PT) occurs more than once for a subject during the treatment period, the maximal severity is taken into account.

## 10.9.2 Deaths and other serious adverse events

### 10.9.2.1 Death

#### All deaths

The number and percentage of subjects who died after the start of the treatment are summarized per treatment group, including the reported causes of death. A listing including all deaths is provided.

#### Fatal SAEs

The following displays of fatal SAEs are provided:

- The number and percentage of subjects with fatal SAEs by treatment group, SOC and PT.

- The number and percentage of subjects with fatal SAEs, by treatment group and PT.
- The number and percentage of subjects with related fatal TEAEs by treatment group and PT.

Fatal SAEs are included and flagged in the listing of all SAEs.

#### ***10.9.2.2 Serious adverse events***

The following displays of SAEs are provided:

- The number and percentage of treatment-emergent SAEs, and subjects experiencing treatment-emergent SAEs, by period of onset (on Day 1 post-dose, after Day 1, overall), treatment group, SOC and PT.
- The number and percentage of subjects with treatment-emergent SAEs by treatment group and PT.
- The number and percentage of subjects with related treatment-emergent SAEs, by treatment group and PT. If an adverse event (PT) occurs more than once for a subject during the treatment period, the strongest relationship to study treatment is taken into account.

A listing including all SAEs is provided.

#### ***10.9.2.3 Adverse events leading to study treatment discontinuation***

The following displays of TEAEs leading to study treatment discontinuation are provided:

- The number and percentage of subjects experiencing TEAEs leading to study treatment discontinuation, by period of onset (on Day 1 post-dose, after Day 1, overall), treatment group, SOC and PT.
- The number and percentage of subjects with TEAEs leading to study treatment discontinuation by treatment group and PT.
- The number and percentage of subjects with related TEAEs leading to study treatment discontinuation, by treatment group and PT

A listing including all AEs leading to study treatment discontinuation is provided.

#### ***10.9.2.4 Other significant adverse events***

The number and percentage of subjects who experienced after the first study treatment at least one adverse event of special interest (AESI), at least one AESI within each category and at least one AESI within each preferred term is summarized by treatment group.

The relative risk of having a specific AESI in each dose group compared to placebo is summarized in a table and presented in a figure (forest plots).

A listing including all AESIs is provided.

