#### **11.4.3 Analysis of the safety variable(s)**

The Safety Analysis Set will be used to perform all safety analyses.

If not otherwise stated, only treatment-emergent safety data (observations with onset or assessment dates at/after first intake of study drug up to 6 weeks after study drug discontinuation) will be considered in tables and figures. All safety data will be included in listings, with flags for safety data not considered to be treatment-emergent.

Specific safety events (AEs, laboratory tests, ECG findings, etc.) will be considered. In general, they consist of one or more well-defined safety events that are similar in nature and for which there is a specific clinical interest in connection with ACT-334441.

For specific AESIs, the number and percentage of subjects with at least one event will be reported. Point estimates and 95% CIs for safety-event incidences and the relative risk ratio relative to placebo will be provided without adjustment for multiplicity.

Exploratory analysis of time to first onset of safety events of interest may be displayed by Kaplan-Meier estimates. Subjects not experiencing the safety event will be censored at the minimum of the EOS date and 6 weeks after last dose of study drug. Where applicable, study treatment doses will be compared with placebo by hazard ratios and corresponding 95% CIs from Cox's regression model.

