#### *11.4.3.1.3 AESIs*

The number and percentage of subjects who experienced at least one AESI, at least one AESI within each category and at least one AESI within each preferred term will be summarized by dose. The relative risk of having an AESI in each dose group compared to placebo will be summarized using forest plots.

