### 11.6 Sample size

#### 11.6.1 Sample size justification

[figure not shown]
The sample size for the study was determined based on simulations. A sample size of 64 subjects (12 in each ACT-334441 dose group of 0.5 mg, 1 mg, 2 mg, 4 mg and 16 in the placebo group) would provide an average power of at least 90% to show a significant dose-response relationship at a one-sided alpha significance level of 5%, under the assumption of a lymphocyte % reduction compared to baseline of 0% (mean at Week 12 =  $2.0 \times 10^9/L$ ) for placebo and a maximum of 70% for any ACT-334441 dose (mean at Week 12 =  $0.6 \times 10^9/L$ ). A maximum lymphocyte % reduction compared to baseline of 70% was assumed based on results obtained in Phase 1 with ACT-334441 and with other S1P modulators. The pooled standard deviation is assumed to be  $0.45 \times 10^9/L$ . This takes into account 10% of subjects being excluded from the PDS.

If Part B is not conducted and the 4 mg dose is not tested then there will be an average power of at least 80% to show a significant dose-response relationship with three doses at a one-sided significance level of 5%, using the same assumptions as above (based on a total sample size of 48 subjects [12, 12, 12 and 12 in placebo, 0.5 mg, 1 mg and 2 mg, respectively]).

Assuming a % reduction in lymphocyte counts of between 25% to 70% (and pooled standard deviation =  $0.45 \times 10^9/L$ ) compared to placebo, any single pairwise dose comparison will have between 77% and 100% power to detect a difference at a 2-sided significance level of 5%.

Assumptions on the placebo response rate, maximum effect sizes and candidate dose-response models are based on the observed lymphocyte counts in study AC-064-101.

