### Part B

Part B consists of two parallel treatment groups (including 4 mg ACT-334441 and placebo control).

Approximately 16 subjects were randomized (3:1) via an IRT system to one of the two groups (i.e., 12 subjects receiving 4 mg ACT-334441 and 4 subjects receiving placebo o.d.). Subjects enrolled in Part A were not eligible for Part B.

The study design is shown in [Figure 1](#).

**Figure 1** Study design of AC-064A201 investigating ACT-334441 in SLE subjects

EOT = End-of-Treatment; EOS = End-of-Study; FU = follow-up; IDMC= Independent Data Monitoring Committee.

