### 5.8.5 Other significant adverse events

#### 5.8.5.1 AE of special interest

An AE is considered to be an AE of special interest (AESI) if it is treatment emergent and belongs to any of the categories listed below (the list of corresponding MedDRA PT is defined in the latest AESI list enclosed in [Appendix 15.2.2](#)):

- Effect on heart rate and rhythm AESI (including hypotension)
- Cardiovascular AESI
- Hypertension AESI
- Liver AESI (Hepatobiliary disorders/ liver enzyme abnormality)
- Pulmonary AESI
- Macular edema AESI
- Infection AESI
- Herpetic infections AESI
- Skin malignancy AESI
- Non-Skin malignancy AESI
- Stroke AESI
- Seizure AESI

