## 10 STATISTICAL ANALYSES

This study is performed in two parts: part A with four treatment groups (including 0.5 mg, 1 mg, or 2 mg of ACT-334441 and placebo control) and part B with two treatment groups (including 4 mg of ACT-334441 and placebo control). In all analyses the assumption is made that the data from part A and part B can be combined, in particular the subjects randomized to placebo in any part of the study are analyzed as one group. This assumption is investigated for the main pharmacodynamics endpoint in a sensitivity analysis.

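### AESIs are compared with placebo only by the relative risk, with no interval method or zero-cell rule; at 12 versus 16 subjects and low event rates it often has no usable value, so a risk difference should be added beside it.

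*SAP*

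**What the plan says.** SAP 10.9.2.4 summarises the number and percentage of subjects with an AESI by treatment group: overall, by category and by preferred term. It then gives the comparison: "The relative risk of having a specific AESI in each dose group compared to placebo is summarized in a table", with a forest plot, and lists all AESIs. It plans no risk difference, no interval for the relative risk and no convention for empty arms.

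The protocol uses the same measure. Section 11.4.3.1.3 states: "The relative risk of having an AESI in each dose group compared to placebo will be summarized using forest plots". Section 11.4.3 goes further than the SAP on precision: "Point estimates and 95% CIs for safety-event incidences and the relative risk ratio relative to placebo will be provided without adjustment for multiplicity". It names no method for these intervals either.

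The planned sizes are "12 in each ACT-334441 dose group of 0.5 mg, 1 mg, 2 mg, 4 mg and 16 in the placebo group" (Protocol 11.6.1). Placebo is pooled across Parts A and B: SAP 10 says that "the subjects randomized to placebo in any part of the study are analyzed as one group". SAP 5.8.5.1 counts an event as an AESI if it is treatment-emergent and "belongs to any of the categories listed below"; 12 categories follow.

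**The concern.** A ratio of two proportions behaves badly when an arm has no events. If the dose arm is empty the ratio is 0, if placebo is empty it is infinite, and if both are empty it is 0/0. The usual interval on the log scale fails in all three cases, and none of the three can be placed on a log-scale forest plot. With arms of 12 and 16 and some categories that should be rare, this will be frequent.

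Safety and tolerability is a main objective of the study. A pattern such as 3/12 on a dose against 0/16 on placebo, which a safety reader most wants quantified, would have no finite value of the only planned comparative measure. Without a stated rule, the choice between a blank, an infinity sign and an ad hoc continuity correction could be made after unblinding.

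**Working it through.** **Inputs.** Part A randomises 48 subjects 1:1:1:1, so 12 to placebo. Part B has "12 subjects receiving 4 mg ACT-334441 and 4 subjects receiving placebo o.d". Pooled placebo is 12 + 4 = 16 and the total is 4 × 12 + 16 = 64, which reproduces Protocol 11.6.1. Twelve categories × four doses give 48 category-level relative risks. No AESI rate appears in either document, so the rates below are assumptions.

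**Chance that the sample relative risk is zero, infinite or undefined.** With true rate p in both arms:

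P(at least one empty arm) = 1 − [1 − (1−p)^12] × [1 − (1−p)^16]

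P(placebo empty) = (1−p)^16; P(both empty) = (1−p)^28

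| Rate p | (1−p)^12 | (1−p)^16 (placebo empty) | At least one arm empty | Both empty |
|---|---|---|---|---|
| 2% | 0.785 | 0.724 | 94% | 57% |
| 5% | 0.540 | 0.440 | 74% | 24% |
| 10% | 0.282 | 0.185 | 42% | 5% |
| 20% | 0.069 | 0.028 | 9.5% | 0.2% |

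For example, at 5%: 1 − 0.460 × 0.560 = 0.743. The probability of at least one empty arm passes 50% at p ≈ 8.5%.

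The same placebo group serves all four doses. An empty placebo arm therefore removes all four finite relative risks for that category at once: 72% of the time at 2%, 44% at 5% and 19% at 10%.

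**Unequal rates.** At 20% on a dose against 5% on placebo: 1 − (1 − 0.8^12)(1 − 0.95^16) = 1 − 0.931 × 0.560 = 48%. At 30% against 10%: 20%.

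**Why the usual interval fails.** The log-scale standard error is √(1/x₁ − 1/n₁ + 1/x₂ − 1/n₂), which needs x₁ > 0 and x₂ > 0.

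**The risk difference with Newcombe's interval.** This combines the two Wilson intervals. For 3/12 against 0/16, the Wilson limits are 0.089 to 0.532 and 0 to 0.194:

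- lower: 0.25 − √[(0.25 − 0.089)² + (0.194 − 0)²] = 0.25 − 0.252 = −0.002
- upper: 0.25 + (0.532 − 0.25) = 0.532

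The result is +25.0 points (−0.2 to +53.2). Others:

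- 1/12 against 0/16: +8.3 (−12.2 to +35.4)
- 0/12 against 1/16: −6.3 (−28.3 to +18.5)
- 0/12 against 0/16: 0 (−19.4 to +24.2)

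Over all 13 × 17 = 221 possible tables, the estimate is finite and the interval has positive width in every one. A Wald interval has zero width in four of them, including 0/12 against 0/16.

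**Why the method must be named.** For 3/12 against 0/16, a standard library score interval for the difference runs from +2.3 to +53.7 points and excludes zero, while Newcombe's just includes it. The same library routine returned an error at 0/12 against 0/16, 1/12 against 0/16 and 0/12 against 1/16.

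**The case against.** The strongest reply has four parts.

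1. **Rates.** A reader might infer that most AESI categories, or most lines of the forest plot, would be unusable. The documents do not support that. They give no AESI rates, and the 50% mark needs a rate below about 8.5%. Several categories are broad in SAP 15.2.2: heart rate and rhythm also takes in syncope and hypotension terms, liver uses a comprehensive query, and pulmonary adds dyspnoea and lung-function terms. Rates there could be well above 10%. This stands. Low rates are plausible for stroke, seizure, malignancy, macular edema and infections counted only if serious or severe, but they remain an assumption.

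2. **A zero ratio is still a number.** 0/12 against 1/16 gives a relative risk of 0, and score intervals exist with one empty arm: 0 to 5.0 there, and 0.35 to infinity for 1/12 against 0/16. This also stands. Only 0 against 0 carries no information on the ratio. But the SAP specifies no such interval, and a point at 0 or infinity still has no place on a log axis.

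3. **Nothing is hidden.** A reader might infer that a signal such as 3/12 against 0/16 would be missed. It would not: counts and percentages are tabulated, all AESIs are listed, the safety analysis is mainly descriptive, and no decision rule uses the relative risk. The loss is confined to the comparative estimate and its precision.

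4. **The remedy adds little, and the protocol chose the ratio.** The intervals are wide, and the protocol states that "the relative risk ratio relative to placebo will be provided without adjustment for multiplicity". This argues against replacing the ratio. It does not argue against adding a difference beside it: an interval of about −19 to +24 points at 0 against 0 usefully shows how little the absence of events rules out.

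The output shells are not in the text available here, so a footnote convention for non-estimable ratios may exist there.

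**Conclusion.** The point holds as a gap in the comparative display, conditional on event rates. With planned arms of 12 and 16 and equal true rates, the only planned between-group AESI measure is zero, infinite or undefined in 94%, 74%, 42% and 9.5% of comparisons at rates of 2%, 5%, 10% and 20%. An empty placebo arm leaves all four doses without a finite value.

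These figures rest on assumed rates and planned sizes; actual Safety Set sizes may differ. The documents do not establish that most categories will be affected, that the plot will be largely blank, or that the relative risk must be abandoned. The SAP itself cites small dose groups as the reason to drop subgroups (Section 8), and it assigns Clopper-Pearson intervals to the ECG, liver-test, blood-pressure and spirometry proportions, but no interval to AESIs. This is a cheap improvement, not a flaw that threatens the study's conclusions.

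**What to change.** In SAP 10.9.2.4:

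- Add the risk difference of each dose versus pooled placebo to the AESI table and forest plot, with a 95% interval whose method is named in advance. Newcombe's is suitable; Wald is not.
- Keep the protocol's relative risk, with a named interval method, where both arms have events. Show it as not estimable when either arm has none, with the counts alongside. A ratio of 0 could be printed, but one rule for any empty arm is simpler and matches what can be plotted.
- Apply no continuity correction unless it is specified before unblinding.

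The cost is a few sentences of SAP text and a routine programming step. The downsides are one added measure that the protocol does not name, and wide intervals. Newcombe's is also conservative when events are rare: coverage is about 99.9% at 5% in both arms and 98.9% at 10%.

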### **10.9.3 Electrocardiography (ECG)**

#### ***10.9.3.1 12-lead ECG variables and findings***

The following displays of ECGs are provided:

- Quantitative descriptive statistics for absolute values of ECG parameters by treatment group and analysis visit and time point.
- Quantitative descriptive statistics for the absolute change from baseline to 1h, 2h, 3h, 4h, 5h and 6 h post-dose on Day 1 and each post-baseline analysis visit by treatment group and parameter.
- Boxplots of absolute values at baseline and all post-baseline analysis visits and time points: one figure per parameter and per treatment group. Notable abnormality thresholds are displayed on the plots as an overlay.
- Notable ECG abnormalities for QTcB, QTcF, HR, PR and QRS are summarized by treatment group by presenting the number and percentage of subjects with any abnormality at each post-baseline analysis visit and time point, at any time on Day 1 (from 1 hour post-dose to discharge), at any time after Day 1 (from discharge on Day 1 up to EOT), and at any time post-baseline (from 1 hour post-dose to EOS), 95% Clopper-Pearson confidence intervals are presented for the proportions.
- The number and percentage of subjects with any treatment-emergent ECG qualitative abnormalities at any time (ECG findings) by category and reported term are summarized by treatment group.

The denominator for percentages is the number of subjects with at least one post-baseline assessment in the considered interval.

All ECG data (parameters and findings) are listed by treatment group, subject and visit. All post-treatment notable abnormalities are flagged and qualitative abnormalities (as transferred by the ECG central reader) are listed.

#### ***10.9.3.2 24 hour Holter-ECG***

Quantitative descriptive statistics are presented for the hourly mean heart rate (bpm) by time interval for measurements performed on Visit 2 (Randomization/ Day 1).

The hourly records are time-matched between Visit 1 (Screening) and Visit 2 (Randomization/ Day 1) and quantitative descriptive statistics for the corresponding change by time interval are presented.

The evolution of the values over time for the hourly mean heart rate (bpm) on Visit 2 (Randomization/ Day 1) is provided in graphical format (mean and 95% CI for the absolute value for each time interval and treatment group).

The evolution of the change from time-matched screening holter on day 1 for the hourly mean heart rate (bpm) is similarly provided in a graphical format (mean and 95%CI for the time-matched change for each time interval and treatment group)

Treatment-emergent Holter-ECG findings are tabulated by treatment group.

All Holter-ECG data are listed by treatment group, subject and visit. A listing of all Holter-ECG abnormalities is also provided.

#### 10.9.4 Laboratory tests

Descriptive summary statistics by analysis visit and treatment group are provided for observed values and absolute changes from baseline by category (hematology/ coagulation, chemistry, urinalysis). Data are displayed in SI units as provided by the central laboratory.

Values from local labs are not included in the different summaries but are included in the listings.

For categorical urinalysis parameters (dipstick), qualitative descriptive statistics for recorded values are presented by parameter and visit.

Treatment-emergent laboratory abnormalities are summarized by lab category, parameter and severity over the study treatment period. For each parameter, the severity is based on the position of the value against reference ranges (central laboratory) and additional thresholds for significance (see appendix 7 of the study protocol) and the worst abnormality is considered in each direction separately (Low and High). In addition, for the liver tests, the number and percentages of subjects with values above the normal ranges, or with abnormal values that are of a certain size (e.g., twice the upper limit of the normal ranges; see section 5.1.10.5, figure 3 of the study protocol) are presented along with their 95% Clopper-Pearson confidence intervals. For each parameter, the maximum highest value recorded during the treatment period is taken into account.

The denominator for percentages is the number of subjects with at least one post-baseline assessment.

All data are presented in the listings:

- hematology, chemistry, coagulation, urinalysis
- urinary dipstick
- viral serology (if assay is required)/ tuberculosis test results are listed along with the other baseline characteristics

- serum and urinary pregnancy tests results are listed along with the childbearing potential information

